#### 17.9 Efficacy Analyses

# 17.9.1 General Efficacy Analysis Methodology

Unless otherwise specified, all the efficacy analyses for the DBP will be based on the FAS. All endpoints will be presented with descriptive statistics and the one-sided 95% confidence intervals for both absolute values and change from baseline. Histograms will be explored and presented for the UMSARS scores observed cases; otherwise only in case of compromising findings for the secondary endpoints.

Since the primary, key secondary and selected secondary analyses for the UMSARS scores will be performed in a Bayesian framework, the success threshold for the Bayesian posterior probability of superiority relative to placebo will be calibrated through simulations to correspond to a significance level of 5% evaluated one-sided. For the frequentist analyses, the significance level will be 5%, which will be applied one-sided.

A testing strategy will be applied including the primary analysis on UMSARS TS and the key secondary analysis on mUMSARS to protect the type I error for these analyses. Further details in the section 17.9.4, Testing Strategy.

Efficacy analyses for the OLE will be exploratory based on the OLES. All patients in the OLE will receive active treatment. However, patients receiving placebo in the DBP and hence switching treatment will be defined and handled as a separate group.

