The following analysis sets will be used for the analyses:

- *all-patients-randomized set* (APRS) all randomized patients
- *all-patients-treated set* (APTS) all patients in the APRS who took at least one dose of double-blind IMP
- *full-analysis set* (FAS) all patients in the APTS who had a valid baseline assessment and at least one valid post-baseline assessment of the UMSARS TS, prior to, or at withdrawal from treatment
- *PK sub-set* (PKS) all patients in the APTS with quantifiable plasma or CSF concentration of Lu AF82422
- *Sensor-based subset* (SBS) all patients in the APTS who consented to wear at least one of the included sensor-based devices and who had a valid baseline assessment and at least one valid post-baseline assessment, where 'valid assessment' covers that gait parameters can be derived within the observation period
- *Exit Interview subset* all patients in the FAS having a complete Exit interview with the patient and/or the caregiver
- *Study Experience subset* all patients in the FAS having a complete Study Experience interview with the patient and/or the caregiver
- *Open-label treatment extension set* (OLES) all patients in the FAS who consented to participate in the OLE and who had at least one dose of Open-Label IMP for the OLE

All data from the Placebo-controlled Period will be cleaned and the database for the DB-Period will be locked when there are no more patients in the DB-Period. The patients and data will be classified into the analysis sets according to these definitions at a Classification Meeting held after the database containing all efficacy measures from the DB-Period has been released but before unblinding of the study.

Demographics, baseline characteristics and baseline efficacy variables will be summarized based on the APTS and on the OLES, respectively.

The efficacy analyses for the DB-Period will be based on the FAS. Analyses for the Extension Period will be based on the OLES.

Safety outputs (including exposure and concomitant medications) will be based on APTS in the DB-Period and OLES for the Extension Period, respectively. Relevant safety outputs for data collected during the Safety Follow-up Period for participants not entering the OLE will be based on the APTS.

Listings will be based on the APTS.

6 Descriptive Statistics

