14.2 General Efficacy Analysis Methodology

Unless otherwise specified, all efficacy analyses will be based on the FAS for the observed case (OC) data.

For endpoints analysed in the Bayesian framework, the success threshold for the Bayesian posterior probability of superiority relative to placebo [Prob(θ <1)] has been calibrated using simulations to correspond to a significance level of 5% applied one-sided. By doing so a success threshold of 0.975 has been identified which will be used to evaluate the primary endpoint and remaining endpoints evaluated by the Bayesian progression model. A burn-in of 1000 samples will be used for the Bayesian analysis.

All statistical tests of the secondary efficacy endpoints will be presented two-sided on a 5% significance level.

A testing strategy will be applied including the primary analysis on UMSARS TS and the key secondary analysis on mUMSARS to protect the type I error on an overall one-sided 5% significance level for these analyses. Further details to be found in chapter 15.

For analysis of exploratory efficacy data collected in the open-label extension, the original placebo patients will be presented as a separate group and hence there will be no pooling of treatment groups.

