14.3.3 Rationale for Selected Analysis Method for the Primary Endpoint

It is believed, that applying the Bayesian progression model is an appropriate and powerful way of analysing MSA disease progression data in this context, since:

- The Bayesian methodology provides relatively simple computational and interpretable posterior probabilities for decision-making. In addition, it offers a robust performance in relation to convergence, as well as consistency across the performed analyses.
- There is a strong indication based on available 12-24 months MSA progression data¹ (i.e., UMSARS total and part I scores) of a steep and nearly linear disease progression trajectory; especially for the earlier patient segment, making it meaningful to talk about a change in the slope or a slowing down of progression.
- Due to the parametrization of effect expressed common across all visits, the model offers an easy interpretable target of estimation being the percentage-wise slowing in progression through up to 72 weeks treatment for Lu active dose compared to placebo.
- Based on the Lu AF82422 hypothesized mechanism of action, an early trend in UMSARS in favor of Lu AF82422 is reasonable due to the expected immediately steep MSA progression curve. Furthermore, the UMSARS is assessed for the first time at Week 12 following multiple dosing allowing time for initial treatment manifestation. Assuming that such an early trend will be further substantiated over time in a proportional-like manner due to the hypothesized moderation of the MSA pathology by Lu AF82422 (i.e., inhibition of seeding of pathological form(s) of alpha-synuclein, inhibition of the C-terminal proteolytic cleavage of alpha-synuclein, and potential immune-mediated clearance of alpha-synuclein/mAb complexes by the active Fc region), it seems less likely that the effect will significantly wear-off within the up to 72 weeks treatment period.
- The progression model is better suited for handling individual differences in treatment duration (i.e., when having differences in treatment duration due to the study design or a notable number of drop-outs/deaths); despite incomplete data (<72 weeks), a slope can still be estimated making full use of all patients. In particular, the long duration of the study (48-72 weeks) makes it more relevant to consider the effect integrated over time instead of the change from baseline for a single chosen timepoint.

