14.3.5 Sensitivity Analyses of the Primary Endpoint

Handling of Missing Data

The following sensitivity analyses will be performed in case of drop-out/withdrawal/death, where the below rules will be applied for the visit following the event for subjects not having

complete data from the Withdrawal Visit, assuming that intermediate missingness will be 'missing at random':

- For withdrawal due to death, impute individual missing UMSARS items as worst possible score in case of death.
- For withdrawal due to other reasons, impute individual missing UMSARS items as worst observed within-subject value for the specific item at any post-IMP time point.
- For withdrawal due to other reasons, impute individual missing UMSARS items as the worst value observed within the combined treatment and control arms at any post-IMP time point.

Two analyses will be performed in both cases using the above strategy to handle withdrawal due death. Following each of the above strategies for handling withdrawals due to other reasons will then be applied.

To explore further the impact of death, a non-parametric joint-rank analysis will be performed to account for informatively missing data by ranking patients based jointly on their Week 48 UMSARS score (UMSARS TS and mUMSARS) and 48-week survival, i.e., time-to-death. Such analysis corresponds to a composite strategy. In case of missing Week 48 data for survivors, Multiple Imputation (MI) will be performed in which the remaining missing data will be imputed corresponding to a missing-at-random assumption.

Missing data for UMSARS Week 12 up to Week 48 will be addressed by using Multiple Imputation. Missing data will be imputed using a sequential regression-based multiple imputation method, based on the imputation models established from the corresponding randomized treatment group. Example SAS code for this imputation can be found in Appendix II.

200 imputed datasets will be created, which will each be analysed and combined as follow.

Define score, u_{ij} , which is chosen to reflect whether patient i has had the more favourable UMSARS score than patient j. In the case where both patient i and j died prior to the Week 48 assessment:

- $u_{ij} = 1$ in the case where patient i died after patient j
- $u_{ij} = -1$ in the case where patient i died before patient j
- $u_{ij} = 0$ in the case where it cannot be determined who died first

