24.2.1 UMSARS and additional efficacy COAs

For UMSARS, both a narrow and a broad approach will be applied for assigning observations to a visit: 1) observations will be mapped to the nearest official clinical visit in 4-weeks intervals, independent whether UMSARS originally was scheduled for this visit, and 2)

observations will be mapped to the nearest official UMSARS visit in 12-weeks intervals according to protocol.

Nominal Vis Number (DB-Period)	Nominal Vis Week	Nominal Vis Day	Time Window narrow ¹	Time Window broad ¹
V1 (Screening Visit)	-6	-42	NA	NA
V3 (Baseline Visit)	0	0	-7 to 7	-7 to 7
V5 (WD Visit)	4	28	15 to 42	NA
V7 (WD Visit)	8	56	43 to 69	NA
V9 (planned UMSARS/WD Visit)	12	84	70 to 98	15 to 126
V10 (WD Visit)	16	112	99 to 126	NA
V11 (WD Visit)	20	140	127 to 154	NA
V12 (planned UMSARS/WD Visit)	24	168	155 to 182	127 to 210
V13 (WD Visit)	28	196	183 to 210	NA
V14 (WD Visit)	32	224	211 to 238	NA
V15 (planned UMSARS/WD Visit)	36	252	239 to 266	211 to 294
V16 (WD Visit)	40	280	267 to 294	NA
V17 (WD Visit)	44	308	295 to 322	NA
V18 (planned UMSARS/EoTDBP/WD Visit)	48	336	323 to 350	295 to 378
V19 (EoTDBP/WD Visit)	52	364	351 to 378	NA
V20 (EoTDBP/WD Visit)	56	392	379 to 406	NA
V21 (planned UMSARS/EoTDBP/WD Visit)	60	420	407 to 434	379 to 462
V22 (EoTDBP/WD Visit)	64	448	435 to 462	NA
V23 (EoTDBP/WD Visit)	68	476	463 to 490	NA
V24 (planned UMSARS/EoTDBP Visit)	72	504	491 to 518	463 to 518
Nominal Visit Number (OLE-Period)				
V1E (baseline OLEP Visit) ²	0E	0	-7 to 7	-7 to 7
V2E (WD Visit)	4E	28	15 to 42	NA
V3E (WD Visit)	8E	56	43 to 69	NA
V4E (planned UMSARS/WD Visit)	12E	84	70 to 98	15 to 126
V5E (WD Visit)	16E	112	99 to 126	NA
V6E (WD Visit)	20E	140	127 to 154	NA
V7E (planned UMSARS/WD Visit)	24E	168	155 to 182	127 to 210
V8E (WD Visit)	28E	196	183 to 210	NA
V9E (WD Visit)	32E	224	211 to 238	NA
V10E (planned UMSARS/WD Visit)	36E	252	239 to 266	211 to 294
V11E (WD Visit)	40E	280	267 to 294	NA
V12E (WD Visit)	44E	308	295 to 322	NA
V13E (planned EoTOLE Visit)	48E	336	323 to 350	295 to 350

Panel 16 Visit Windows for UMSARS

All post-baseline visits (except EoT visits) can be converted into a Withdrawal (WD) Visit. ¹ For DBP and OLEP, respectively, the applied narrow window will be continuous (i.e., ± 14 days) to avoid invalid assessments (protocol text ± 3 days). The broad window is set up as continuous as well to match. ² EoTDBP Visit will work as Baseline Visit for the OLEP if done within the acceptable window.

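### Deaths with no post-baseline UMSARS fall outside the FAS, so the SAP's death-based sensitivity analyses leave out patients they would rank worst

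*SAP*

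**What the plan says.** **Default set.** SAP 14.2: "Unless otherwise specified, all efficacy analyses will be based on the FAS for the observed case (OC) data". Protocol 17.9.1 agrees: "Unless otherwise specified, all the efficacy analyses for the DBP will be based on the FAS".

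**FAS.** SAP section 5 admits a treated patient with a valid baseline and "at least one valid post-baseline assessment of the UMSARS TS, prior to, or at withdrawal from treatment". Protocol 17.3 has the same rule in substance.

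**First assessment.** SAP 14.3.3: "the UMSARS is assessed for the first time at Week 12 following multiple dosing allowing time for initial treatment manifestation". An earlier UMSARS can arise only at a Withdrawal Visit. Panel 16 (SAP 24.2.1) lists Weeks 4 and 8 for that purpose, with the note "All post-baseline visits (except EoT visits) can be converted into a Withdrawal (WD) Visit".

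**Death analyses.** SAP 14.3.5 has two devices for death. One imputes the worst possible item scores at the visit after death. The other is introduced so: "To explore further the impact of death, a non-parametric joint-rank analysis will be performed". It compares every pair of patients. A death before Week 48 loses to any survivor, and of two deaths the earlier one loses. The SAP labels this a composite strategy. Neither device has its own analysis set in the visible text. SAP 14.4.1 carries both over to mUMSARS.

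**Deaths as a safety outcome.** SAP 16.9 summarises deaths by treatment group, with a Kaplan-Meier plot and, if applicable, a Cox model. The 16.2 default puts these on the APTS.

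**The concern.** The joint-rank analysis exists because death makes the missing UMSARS informative, and it treats an early death as the worst outcome a patient can have. The default set removes some of those deaths before ranking starts. The analysis then describes only patients who lived long enough, or withdrew in an orderly enough way, to be rated once after baseline. The worst-score imputation has the same gap, because a patient outside the FAS has no record to impute into.

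Protocol 17.9.3 directs these sensitivity analyses particularly at deaths and at drop-outs without follow-up data, so the default set works against their stated purpose. If such deaths were unequal between arms, the composite result would be tilted towards the arm that had more of them.

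**Working it through.** **Step 1: who is lost.** The rules, applied to three treated patients:

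| Patient | Post-baseline UMSARS before or at withdrawal | In FAS | Ranked as a death |
|---|---|---|---|
| Dies after the Week 12 rating, before Week 48 | Yes | Yes | Yes |
| Withdraws before Week 12, rated at a Withdrawal Visit, then dies before Week 48 | Yes | Yes | Yes |
| Dies with neither rating | No | No | No |

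SAP 24.1.1 assigns a worst score after death, but this does not bring the third patient in. It is a derived value placed at the visit following the death, not an assessment made before or at withdrawal.

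**Step 2: scale of the joint-rank score.** Inputs are N = 60, split 40 to 20 (SAP section 21), and the pairwise rule in 14.3.5. Without ties the scores have

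- SD = sqrt((60² - 1)/3) = 34.6
- SE of the arm difference = 34.6 × sqrt(1/40 + 1/20) = about 9.5

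**Step 3: effect of one omitted death when treatment does nothing.** Ranked last of 60, the patient scores -59, and each of the other 59 gains +1 from that comparison. The difference is active minus placebo, and a higher score is better.

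- Death on active: active mean (-59 + 39)/40 = -0.5 and placebo mean +1. The difference is -1.5 and t is about -1.5/9.5 = -0.16.
- Death on placebo: placebo mean (-59 + 19)/20 = -2 and active mean +1. The difference is +3 and t is about 3/9.5 = +0.32 (0.31 if only the death's own share, 59/20 = 2.95, is counted).

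With the patient dropped, the expected difference is 0. These figures are shifts in the arm difference, not in one arm's mean.

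**Step 4: the same question when there is an effect.** The SAP's 75% power cannot be reproduced, because the progression and variance inputs are not in the visible text. Back-solving a simple two-group comparison at one-sided 5% with 40 and 20 patients gives a standardized effect of about 0.635. I simulated the joint-rank t-test 4,000 times per scenario at that value, with complete data and no multiple imputation:

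| Early deaths with no UMSARS | Power if ranked | Power if dropped | Mean change in t from dropping |
|---|---|---|---|
| 1 active | 65% | 72% | +0.24 |
| 2 active | 55% | 72% | +0.47 |
| 1 placebo | 79% | 70% | -0.28 |
| 2 placebo | 86% | 70% | -0.56 |

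Dropping the death helps the arm in which it occurred in every row.

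**Step 5: how often it could arise.** The documents give no early mortality rate. If the risk of such a death were 0.5%, 1% or 2% per patient (assumed), the chance of at least one among 60 would be 1 - (1 - p)^60 = 26%, 45% or 70%, with 0.3, 0.6 or 1.2 expected.

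I have not sized the effect on the worst-score imputation, for want of the inputs named in step 4.

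**The case against.** The best counter-argument is that little depends on this. The joint-rank analysis is a sensitivity analysis outside the fixed sequence in SAP 15.2, and no success rule uses it. Entry requires an anticipated survival of at least 3 years, a UMSARS Part I score of 16 or less and age 75 or under (Protocol 6.3), so deaths this early should be few. Keeping sensitivity analyses on the primary set also isolates the effect of the missing-data assumption, whereas a move to the APTS changes population and method together. All of this stands, and it limits the importance of the point. It does not remove the bias, because the omitted outcome is the one the ranking was built to include.

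A reader might infer that everyone who dies before Week 12 is excluded. The documents do not say so: a patient rated at an earlier Withdrawal Visit stays in the FAS.

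A reader might also infer that an imbalance in early deaths would be hidden. It would not. SAP 16.9 compares deaths by arm on the APTS, adverse events in patients who died are listed for the APRS (16.1.7), and the iDMC sees unblinded serious adverse events as the trial runs (Protocol 11.6.1). Those outputs do not combine death with function, however, so they do not replace the composite analysis.

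The primary estimand, the handling of intercurrent events and the Appendix II code are redacted. Another set could be specified there, so the conclusion rests on the visible text.

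**Conclusion.** The point holds for treated patients who die with no post-baseline UMSARS at all. On the visible text they are excluded from the joint-rank and worst-score death analyses of UMSARS TS and mUMSARS, and the joint-rank result is biased in favour of the arm in which they occur. With no treatment effect, one such death is worth about 0.16 in t on active and about 0.3 on placebo. At the assumed effect of 0.635 the figures are 0.24 and 0.28. The number of such deaths is unknown and probably small, but with 20 placebo patients one is not negligible.

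The documents do not support extending this to the primary result. The primary model uses observed data on the FAS, and nothing here argues against that choice. The point is worth acting on because the cause is a default rule that one sentence can override.

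**What to change.** Add to SAP 14.3.5, before unblinding, that the joint-rank and death-imputation analyses use the APTS. Every death before Week 48 is then ranked by time of death, or given the worst score, whether or not a post-baseline UMSARS exists. The same sentence should cover mUMSARS through 14.4.1. Keep the FAS for the primary model.

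The timing matters: a set chosen after unblinding could be chosen knowing which arm had the early deaths.

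The cost is one sentence and no new data. The downside is a population slightly different from that of the primary analysis, which can be met by also showing the joint-rank result on the FAS. Surviving treated patients with no post-baseline UMSARS could be imputed from baseline and stratification factors, but that is a separate and more debatable choice that this fix does not need.

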14.3 Analysis Methodology for the Primary Endpoint

14.3.1 Primary Analysis of the Primary Endpoint

The primary efficacy analysis following up to 72 weeks of treatment will be based on a Bayesian repeated measures model, also referred to as a Bayesian functional-impairment

progression model (BFPM), of the changes from baseline in the UMSARS TS. The BFPM incorporates the following aspects:

- Repeated measures for the change from baseline in the UMSARS TS score over the recurring 72-week's visit schedule
- Piece-wise linear rate of progression per 12-week time interval. However, does not require equally spaced intervals between observations. Time modelled continuously
- Patient-level random effect in rate of progression
- Proportional treatment effect, θ, for slowing of disease progression rate when treated relative to placebo. In particular, if θ<1, the active treatment slows the rate of progression relative to placebo. If θ>1, the active treatment increases the rate of progression relative to placebo. If θ=1, the rate of progression of UMSARS TS is the same for both active treatment and placebo
- Fixed multiplicative covariate effects in the increase or decrease in the overall rate of
 progression of UMSARS TS for categorized CCI

and region (US and Japan) common across all visits

- Prior distributions for model parameters selected in a conservative and non-informative manner using relatively large outcome spaces
- The primary analysis considers only actual observations and does not impute missing data

Let change from baseline in the UMSARS TS at visit *j* for subject *i* be labelled $Y_{i,j}$, $i = 1, ..., N, j = 1, ..., J_i$ where there are J_i total post-baseline visits for subject *i*. Change from baseline will be modelled as piece-wise linear with time intervals, k = 1, ..., K, defined every 12 weeks. Let $X_{i,j,k}$ be the exposure (time since baseline in weeks) for subject *i* at visit *j* during the time interval *k*. The MSA progression model is:

$$Y_{i,j} \sim N(\mu_{i,j}, \sigma_{t(i)}^2); i = 1, ..., N; j = 1, ..., J_i$$

$$\mu_{i,j} = 0 + \sum_{k=1:K} \left(\beta_k + \beta_{k,i} \right) * (X_{i,j,k}/12) * \theta_{t(i)} * \exp\left(\delta_{g(i)} + \eta_{r(i)} \right)$$

where each parameter is defined below and the prior distribution for the parameter is given:

 β_k : Mean expected change from baseline over each 12-week interval

$$\beta_k \sim Norm(0, 10^2)$$
; $k = 1, \dots, K$

 $\beta_{k,i}$: Subject-level additive random effect in change from baseline over each 12-week interval for subject *i*

$$\beta_{k,i} = \beta_i; \ \beta_i \sim Norm(0, \sigma_\beta^2); \ \sigma_\beta \sim Unif(0, 20)$$

Study 18331A – Statistical Analysis Plan

 θ_t : Multiplicative proportional slowing in rate of progression for treated (t=2) relative to placebo (*t*=1).

$$\theta_1 = 1; \ \theta_2 \sim Unif(0,2)$$

 δ_g : Multiplicative fixed covariate effects for the increase or decrease in rate of progression for plasma NfL level, i.e., missing (g = 3) and high (g = 2) relative to low (g = 1) common across all visits

$$\delta_1 = 0; \ \delta_2 \sim Normal(0, 10^2); \ \delta_3 \sim Normal(0, 10^2)$$

 η_r : Multiplicative fixed covariate effects for the increase or decrease in rate of progression for regions, i.e., Japan (r = 2) relative to US (r = 1) common across all visits

$$\eta_1 = 0; \ \eta_2 \sim Normal(0, 10^2)$$

 σ_t : Measurement error per treatment arm

$$\sigma_t \sim Unif(0,10); t = 1,2$$

The θ_t parameters represent the multiplicative proportional slowing in rate of progression for treated relative to placebo (t=1); also referred to as the functional-impairment progression rate ratio (FPRR). For placebo, the FPRR is assumed to be 1 ($\theta_1 = 1$). Thus, the FPRR parameter for treatment (Lu AF82422) represents the multiplicative change to the mean progression of a placebo patient. If the FPRR is less than 1 then the progression for treatment t is slower than for placebo. A value of FPRR = 0.75 corresponds to a 25% slowing in progression and a value of 0.25 represents a 75% slowing in progression. The errors for the individual observations are modelled as independent normal distributions with a standard deviation of σ .

